- (d) Confirmed increase in serum creatinine of ≥ 0.5 mg/dl (44 $\mu\text{mol/L}$) for patients with baseline creatinine of < 1.4 mg/dl (123 $\mu\text{mol/L}$) or confirmed increase in serum creatinine of ≥ 1 mg/dl (88 $\mu\text{mol/L}$) for patients with baseline creatinine of ≥ 1.4 mg/dl (123 $\mu\text{mol/L}$). Patients with serum creatinine above these values will have their study medication held and a repeated serum creatinine test within 7 days. If serum creatinine is still elevated as specified above (≥ 0.5 mg/dl or ≥ 1.0 mg/dl above baseline), the patient should discontinue the clinical study medication. Otherwise study medication may be resumed unless otherwise contraindicated. For further details please see [Appendix G](#) of this protocol.
- (e) CK >10 x ULN confirmed at a repeated measurement within 24 hours.
- (f) Patients with a central laboratory ALT and/or AST >3 x ULN will be scheduled for a follow-up visit within 3 calendar days following the receipt of the result. See [Appendix H](#) for further guidance.
- Patients should be discontinued from study if the initial and repeat laboratory tests meet any of the following criteria:
- ALT and/or AST are >3 x ULN and TB >1.5 x ULN
 - ALT and/or AST are >5 x ULN for ≥ 14 consecutive days, at any time after initial confirmatory results
 - ALT and/or AST are >8 x ULN
- (g) No longer applicable
- (h) Serum sodium ≤ 125 mmol/l with or without symptoms: dosing of blinded study medication will be interrupted. For further detail please follow instructions stated in [Appendix E](#).
- (i) Haemoglobin ≤ 9.0 g/dl (90 g/l).

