1. CASE IDENTIFICATION AND MANAGEMENT OF DECREASED RENAL FUNCTION

The evaluation of renal function is an important part of the overall safety assessment in the dapagliflozin clinical development program. In order to standardize the definition and management of decreased renal function, the following guidelines has been developed:

- a) **For patients with baseline creatinine of <1.4 mg/dl (123 µmol/L), an absolute increase in serum creatinine level of ≥ 0.5 mg/dl (44 µmol/L) from baseline based on central laboratory results**

- b) **For patients with baseline creatinine of ≥ 1.4 mg/dl (123 µmol/L), an absolute increase in serum creatinine level of ≥ 1.0 mg/dl (88 µmol/L) from baseline based on central laboratory results**

In either of these circumstances, the investigator should consider evaluating the patient for potentially reversible causes of renal dysfunction including but not limited to:

1. concurrent use of NSAIDS, antibiotics, or other medications known to affect measures of serum creatinine
2. volume depletion
3. urinary tract infection
4. obstructive uropathy

Patients should return for repeat central laboratory testing as soon as possible, no later than 7 days after the abnormal result. Study drug should be interrupted pending the results of repeat testing. If after interruption the serum creatinine value remains above the increase limit described above (³0.5 mg/dl or ³1.0 mg/dl above baseline), the patient should permanently discontinue the medication and be withdrawn from the study (in which case an Adverse Event must be reported).

If after study drug interruption the serum creatinine value has decreased to below the increase limit (<0.5 mg/dl or <1.0 mg/dl above baseline), study drug can be re-started if appropriate in the investigator's judgment and after consultation with the study delivery team physician. If study drug is re-started, the patient should return for a follow-up central lab serum creatinine 7-14 days after re-start, although more frequent assessments may be done at investigator discretion. If the patient restarts study drug and the serum creatinine value increases again to the increase limit (³0.5 mg/dl or ³1.0 mg/dl above baseline), the patient should permanently discontinue the medication and be withdrawn from the study (in which case an Adverse Event must be reported).

Clinical Study Protocol Appendix H

Drug Substance	Dapagliflozin
Study Code	D1690C00006
Edition Number	3
Date	

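### The stopping rule prints its 1.4 mg/dl baseline creatinine cut-off as 123 µmol/L, which is not its equivalent, so the two units can assign a baseline of exactly 123 µmol/L to different bands

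*Protocol*

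**What the plan says.** Section 3.3.5.1, item 7(d), splits patients by baseline creatinine. The smaller rise limit, 0.5 mg/dl (44 µmol/L) or more, applies "for patients with baseline creatinine of < 1.4 mg/dl (123" µmol/L). The larger limit, 1 mg/dl (88 µmol/L) or more, applies at or above the same cut-off, again with 123 in brackets. Reaching the limit leads to a drug hold and a repeat test within 7 days. The next condition, "If serum creatinine is still elevated as specified above", restates the rise limits in mg/dl only, and a confirmed rise ends study medication.

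Section 3.3.3 repeats the rule as item 4(d) of the exclusions before extension period II. Appendix G, section 1, uses the same split ("For patients with baseline creatinine of <1.4 mg/dl (123" µmol/L)) and ties it to central laboratory results. The figure 123 appears twice in each of the three places.

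Exclusion 6 in section 3.3.3, which sets creatinine limits at randomization, gives the same 1.4 mg/dl (for women on metformin) as 124 µmol/L. It also prints 1.5 mg/dl as 133 and 2 mg/dl as 177 µmol/L.

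**The concern.** One mg/dl value has two µmol/L equivalents in the current text. In 7(d), 4(d) and Appendix G that value decides which of two rise limits applies, and the limits differ by a factor of two. If the two printed forms of the cut-off are not equivalent, some baseline values fall in one band when read in mg/dl and in the other when read in µmol/L. The rule leads to a hold, then to permanent discontinuation or refusal of extension II if the rise is confirmed. It runs to week 104 at about 150 centres worldwide, and Appendix G exists to make this management uniform.

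**Working it through.** **Inputs.** The printed pairs are 0.5/44, 1/88 and 1.4/123 (section 3.3.5.1, 7(d)) and 1.4/124, 1.5/133 and 2/177 (section 3.3.3, exclusion 6). The protocol states no conversion factor. I assume 88.4 µmol/L per mg/dl, from a molar mass of 113.12 (10,000 / 113.12 = 88.40).

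**Step 1: reproduce the printed figures (mg/dl x 88.4, rounded to nearest).**

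| mg/dl | x 88.4 | Rounded | Printed |
|---|---|---|---|
| 0.5 | 44.2 | 44 | 44 |
| 1.0 | 88.4 | 88 | 88 |
| 1.4 | 123.76 | 124 | 123 (7(d), 4(d), Appendix G); 124 (exclusion 6) |
| 1.5 | 132.6 | 133 | 133 |
| 2.0 | 176.8 | 177 | 177 |

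Every pair is reproduced except 1.4/123.

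**Step 2: could another factor or convention explain 123?** With rounding to nearest:

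- 1.4 = 123 needs a factor below 123.5 / 1.4 = 88.21.
- 1.5 = 133 needs at least 132.5 / 1.5 = 88.33.
- 2 = 177 needs at least 176.5 / 2 = 88.25.

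No single factor meets all three. A factor of 88 gives 123.2, hence 123, but then 132 and 176 for 1.5 and 2. Truncation at 88.4 gives 123, but again 132 and 176.

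**Step 3: the band, with mg/dl unrounded or to two decimals.**

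| Baseline, µmol/L | mg/dl (/ 88.4) | Trigger read in mg/dl | Trigger read in µmol/L |
|---|---|---|---|
| 122 | 1.380 | 44 µmol/L | 44 µmol/L |
| 123 | 1.391 | 44 µmol/L | 88 µmol/L |
| 124 | 1.403 | 88 µmol/L | 88 µmol/L |

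Among whole-number µmol/L values only 123 is split. The split arises within 7(d) itself. Under exclusion 6's conversion, 123 is below the cut-off in both units.

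**Step 4: mg/dl to one decimal.** Here 1.391 becomes 1.4 and 123 falls in the upper band in both units. The disagreement moves to 120, 121 and 122 µmol/L (120 / 88.4 = 1.357 and 122 / 88.4 = 1.380). These report as 1.4 mg/dl but are below 123 µmol/L. The protocol does not state the reporting precision.

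**Step 5: how many patients.** The protocol gives no baseline creatinine distribution. I assume a normal distribution, take the probability of 122.5 to 123.5 µmol/L, and multiply by the 808 randomised patients (section 6.5).

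| Assumed mean, SD (µmol/L) | Probability | Of 808 |
|---|---|---|
| 75, 18 | 0.06% | 0.5 |
| 80, 20 | 0.20% | 1.6 |
| 85, 22 | 0.41% | 3.3 |

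These are patients with that baseline, not changed decisions. A decision changes only if such a patient also has a confirmed rise of at least 44 but below 88 µmol/L.

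**The case against.** The best case for leaving the text alone is that mg/dl is plainly the working unit. Each limit is given first in mg/dl with µmol/L in brackets. The repeat-test clause in 7(d) and the confirmation, restart and second-rise limits in Appendix G are in mg/dl only. Read that way, a baseline of 123 µmol/L has one band. This carries weight, but no sentence says that mg/dl governs, and the cut-off that assigns the band is printed in both units.

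The split also depends on mg/dl being reported to two or more decimals, as step 4 shows. That stands, and the finding is conditional on it.

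The figure may be mere truncation. Section 3.1 prints 180 mg/dl of glucose as 9.9 mmol/l (9.99 untruncated) and 70 mg/dl as 3.8 (3.89). That may explain its origin, but the creatinine pairs in exclusion 6 are not truncated, and a truncated cut-off still disagrees with its mg/dl form.

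The counts in step 5 may be too high. The assumed distributions are untruncated, while exclusion 6 removes low creatinine clearance and so thins the upper tail. Appendix I, section 1.2.5, reports no change in mean or median creatinine at week 12 and increased creatinine in one dapagliflozin subject. Items 2 and 5 of section 3.3.5.1 also allow discontinuation on safety grounds or for a laboratory abnormality. All of this stands and keeps the point small.

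**Conclusion.** The point holds as a conversion error in a threshold that assigns a band. The 123 µmol/L printed in 7(d), 4(d) and Appendix G is not the equivalent of 1.4 mg/dl, and the protocol prints that equivalent differently in exclusion 6. At a baseline of exactly 123 µmol/L, with mg/dl to two or more decimals, the trigger for the hold and repeat test differs twofold by unit. About 0.5 to 3 of 808 patients would have that baseline under the assumed distributions. The number whose management would differ is much smaller and may well be zero.

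A reader might infer more, and the documents do not support it:

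- **That the mismatch with exclusion 6 causes the twofold difference.** Exclusion 6 is an eligibility limit and assigns no band. It only shows that the same value is converted differently elsewhere.
- **That one to three patients would be wrongly stopped or kept on drug.** That would need the confirmed intermediate rise as well.
- **That a rise of 44 or 88 µmol/L is tolerated, or stops treatment at once.** A rise equal to the limit already triggers the rule, and the first step is a hold and retest.
- **That a trial result is at risk.** No efficacy analysis, power figure or error rate depends on this cut-off.

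**What to change.** Reconcile the µmol/L equivalent of 1.4 mg/dl across section 3.3.3 (exclusion 6 and extension II item 4(d)), section 3.3.5.1 item 7(d) and Appendix G, so that both printed units put any given baseline in the same band. Changing only exclusion 6 to 123 would make the figures match but leave the split in place. Which cut-off is clinically intended is for the sponsor to decide. Naming the unit and precision in which the band is assigned would also cover the one-decimal case in step 4. That is a useful addition, not part of the error.

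The cost is a minor text correction to a figure that occurs six times in three places. Section 7.4 requires amendments to be notified to or approved by each ethics committee, so the correction is best carried in the next amendment. No data collection, analysis or sample size changes.

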3.3.5.2 Procedures for discontinuation

Patients who discontinue should always be asked about the reason(s) for their discontinuation and the presence of any adverse events. If possible, they should be seen and assessed by an investigator(s). Adverse events should be followed up; diary cards and investigational products should be returned by the patient.

Patients with an increased CK >10 x ULN will have their study medication held and repeated CK test within 24 hours. If repeated CK is still >10 x ULN the patient should discontinue the study medication. Otherwise study medication may be resumed unless otherwise contraindicated.

Patients with increased liver function tests as defined in section 3.3.5.1 under listings 7(f), will be scheduled for a follow-up visit within 3 calendar days following the receipt of the result. Patients should remain on study medication until the confirmatory results are obtained unless otherwise contraindicated. See CSP [Appendix H - Algorithm on Management of Sustained Elevated Liver Safety Abnormalities](#) for further guidance. If repeated liver function tests still are increased as outlined in section 3.3.5.1 under listings 7(f), the patient should permanently discontinue all study medication and be withdrawn from the study (see CSP [Appendix H - Algorithm on Management of Sustained Elevated Liver Safety Abnormalities](#) for further guidance).

Randomized patients who discontinue before week 104 should complete the procedures described for Visit 18 as soon as possible but at the latest 7 days after discontinuation. These patients should also be scheduled for a follow-up visit (i.e. procedures of Visit 19) 3 weeks after discontinuation of investigational product.

3.3.5.3 Procedures for treatment interruption

In case study treatment was interrupted for more than 7 consecutive days and the restart of study therapy is considered, the investigator must contact the AstraZeneca study team physician to discuss further procedures before restarting study medication.

3.3.5.4 Procedures for handling incorrect enrolled subjects

Patients not meeting the inclusion/exclusion criteria for the study should, under no circumstances, be randomized into the study. If a patient not meeting the study criteria is randomized in error, the patient should complete the study unless there are safety concerns or if the patient withdraws the consent. Data collected for patients randomized in error will be included in the analyses.

3.3.5.5 Procedures for discontinuation from genetic aspects of the study

A patient may withdraw from the genetic research at any time, independent of any decision concerning participation in other aspects of the main study described in this protocol. Voluntary discontinuation by the patient will not prejudice further treatment.

Patients who discontinue from the study should always be asked specifically whether they are also withdrawing or continuing their consent for genetic research. It must be established whether the patient:

- Agrees to the genetic sample and any DNA extracted from the sample being kept for genetic research in the future.

- Withdraws consent for the sample to be kept for genetic research in the future and wishes the sample to be destroyed. Destruction of the sample (or the DNA extracted from the sample) will only be possible as long as the particular sample is traceable. In the event that genetic research has already been performed, AstraZeneca and Bristol-Myers Squibb will retain the results and associated data for regulatory reasons but these will not be used in any subsequent analyses.

The principal investigator is responsible for providing written notification to AstraZeneca and Bristol-Myers Squibb of any patient who has withdrawn consent for the use of the sample taken for genetic research. AstraZeneca and Bristol-Myers Squibb will provide written confirmation to the investigator of the actions taken with the sample, which must be filed in the investigator study file.

3.4 Treatments

3.4.1 Identity of investigational product and comparators

The following investigational products and placebo will be manufactured by Bristol-Myers Squibb Pharmaceutical Research Institute or their designee and distributed by AstraZeneca. The tablets may contain lactose, which may cause discomfort in lactose-intolerant individuals.

Table 3 Investigational product and additional drug

Treatment	Dosage form and strength	Manufacturer
Dapagliflozin	Biconvex, diamond shape, green tablet 2.5 mg (Size: 9 mm)	Bristol-Myers Squibb
Dapagliflozin	Biconvex, diamond shape, green tablet 5 mg (Size: 9 mm)	Bristol-Myers Squibb
Dapagliflozin	Biconvex, diamond shape, green tablet 10 mg (Size: 11 mm)	Bristol-Myers Squibb
Matching placebo for dapagliflozin 2.5 mg and 5 mg	Biconvex, diamond shape, green tablet (Size: 9 mm)	Bristol-Myers Squibb
Matching placebo for dapagliflozin 10 mg	Biconvex, diamond shape, green tablet (Size: 11 mm)	Bristol-Myers Squibb

3.4.2 Doses and treatment regimens

- Dapagliflozin tablets, 2.5 mg, 5 mg and 10 mg, and matching placebos administered orally for the 24-week double-blind treatment period and the 24-week long-term double-blind extension period I. of the study.
- Dapagliflozin tablets, 2.5 mg and 10 mg, and matching placebos administered orally for the 56-week double-blind treatment period II of the study.

Due to different size of tablet, each patients must take 2 tablets once daily to ensure dose blindness. The investigational product dapagliflozin and a matching placebo should be taken once daily as directed by the investigator. The investigational product should be taken at approximately the same time of the day during the study period. Patients should be instructed to abstain from all food and beverages for 12 hours prior to each clinical visit; however, drinking water after midnight is allowed.

3.4.3 Insulin and other background OAD treatment

Patients will be instructed not to take any insulin or OAD medication on the morning of the study visit. In the morning prior to each visit, acceptable concomitant medications can be taken with water only. For further information on insulin- and background OAD treatment please refer to section 3.1.

3.4.4 Labelling

Primary packing of the investigational product will be carried out by Bristol-Myers Squibb or their designee in accordance with current Good Manufacturing Practice (GMP). Labelling of the investigational product will be carried out by AstraZeneca or a Contract Research Organization (CRO) in accordance with current GMP. The labels will be translated into local languages and in accordance with local regulations for each participating country.

All investigational products will be packed in bottles. Each bottle will contain 35 tablets. The labels or booklets for bottles will be translated into local languages. The labels /booklets will fulfil GMP Annex 13 requirements and local regulatory guidelines.

3.4.5 Storage

All investigational products and placebo must be kept in a secure place under appropriate storage conditions. A description of the appropriate storage conditions is specified on the investigational product labels, carton labels, and in the Investigator's Brochure.

3.4.6 Accountability

Investigational products and placebo will only be delivered to the centre when the required regulatory approvals have been obtained. It is the investigator's and/or institution's responsibility to establish a system for handling study treatments as to ensure that:

- Deliveries of products from AstraZeneca or their designee are correctly received by the investigator or his or her designee;
- Such deliveries are recorded on an appropriate drug log

The investigator must maintain accurate records accounting for the receipt and for the disposition of the investigational products and placebo. This record is in addition to any drug accountability information recorded in the electronic Case Report Forms (eCRFs). It must be possible to reconcile delivery records with records of usage and returned stocks. Any discrepancies must be accounted for. Certificates of delivery should be signed by the investigator or a designated person.

The investigator is responsible for making sure that:

- the investigational products and placebo are handled and stored safely and properly (see section 3.4.5)
- the investigational products and placebo are only dispensed to study patients in accordance with this protocol

The investigational products and placebo are to be prescribed only by the investigator. Under no circumstances will the investigator allow the investigational product and placebo to be used other than as directed by the protocol.

Patients must return all unused investigational products and placebo and empty containers to the investigator. The investigator will retain all returned investigational products and placebo, along with any investigational products and placebo not dispensed. At the termination of the Clinical Study or at the request of AstraZeneca, the investigator will either return any unused investigational products and placebo to AstraZeneca, or investigational products and placebo may be destroyed at the study centre depending on local regulations. The return and/or destruction will be documented on a form supplied by AstraZeneca or its designee

3.5 Method of assigning subjects to treatment groups

After written informed consent has been obtained the patient will be assigned a E-code (country, centre, and patient specific). The E-code will be used to identify the patient throughout study participation. Patient eligibility will be established before treatment randomization.

A computer generated, stratified, block randomization schedule, containing stratum, randomization code and treatment, will be provided by AstraZeneca. The randomisation **will** be performed in two strata, one for patients with OADs and one for patients without OADs to ensure approximately equal numbers of patients across the treatment groups within each stratum. The randomization for both strata will be done within balanced blocks. The study medication will be packed according to this schedule.

Subject eligibility will be established before treatment randomization. Randomization to study treatment will be done on Visit 2, in OAD and non OAD strata. Subjects will be randomized strictly sequentially within each stratum, as subjects are eligible for randomization. If a subject discontinues from the study, the subject number will not be reused, and the subject will not be allowed to re-enter the study.

The number and size of tablets will be identical for the investigational products for the 4 treatment arms (applicable until week 12) and for the 3 treatment arms during long term extension period II starting after visit 12. Forced randomization is not allowed. If a patient is dispensed with a wrong drug supply, AstraZeneca must be immediately notified. Corrections for the patient will be made as required. Until resolution, the patient should continue taking study medication, but at the latest until the next scheduled visit.

3.6 Blinding and procedures for unblinding the study

3.6.1 Methods for ensuring blinding

This study will be conducted in a double-blind fashion. All investigational products (dapagliflozin 2.5 mg, 5 mg and matching dapagliflozin 2.5 / 5 mg placebo as well as dapagliflozin 10 mg and matching dapagliflozin 10 mg placebo) are identical in appearance, smell and taste. They will also be packaged into identical bottles. AstraZeneca will provide individual treatment codes, indicating the treatment allocation for each randomized patient.

Until the completion of the 24-week double-blind treatment period, no member of the extended study delivery team at AstraZeneca or Bristol-Myers Squibb, at the investigational centres or any CRO handling data will have access to the randomization scheme, with the exception of the patient safety department and IPS at Bristol-Myers Squibb and AstraZeneca and individual unblinded persons at the central laboratories (Quintiles and Atlanbio). See Section 3.6.2. for further details.

During the long term-double-blind extension period I and II, investigators, patients, and study monitors will continue to be blinded until completion of week 104 without any knowledge of the treatment codes, except for cases of medical emergencies. The treatment codes and knowledge of any results will be strictly kept within AstraZeneca and Bristol-Myers Squibb to safeguard the integrity of the blind of the investigators and patients, and hence to minimize any possible bias in data handling.

